These UPIRSOs/SAEs will be reported to the IRB in accordance with IRB Policy 710, using the appropriate forms found on the website. All related events involving risk but not meeting the *prompt* reporting requirements described in IRB Policy 710 should be reported to the IRB in summary form at the time of continuing review. If appropriate, such summary may be a simple brief statement that events have occurred at the expected frequency and level of severity as previously documented. In lieu of a summary of external events, a current DSMB report can be submitted for research studies that are subject to oversight by a DSMB (or other monitoring entity that is monitoring the study on behalf of an industry sponsor).

7. Plan for reporting adverse events to co-investigators on the study, as appropriate the protocol's research monitor(s), e.g., industrial sponsor, Yale Cancer Center Data and Safety Monitoring Committee (DSMC), Protocol Review Committee (PRC), DSMBs, study sponsors, funding and regulatory agencies, and regulatory and decision-making bodies.

For the current study, the following individuals, funding, and/or regulatory agencies will be notified (choose those that apply):

- All Co-Investigators listed on the protocol.
- Study Grantor (Merck)
- Other Data Safety Monitoring Board (DSMB)
- Yale University IRB

The principal investigator [name] will conduct a review of all adverse events upon completion of every study subject. The principal investigator will evaluate the frequency and severity of the adverse events and determine if modifications to the protocol or consent form are required.

See also DSMB charter attached.

13. Statistical Considerations: Describe the statistical analyses that support the study design.

Variables/Time Points of Interest

The primary outcome is the time to extubation, which will be the duration from arrival to the ICU to the extubation time.

Proposed statistical test/analysis: Positively skewed variables will be log-transformed prior to hypothesis testing. For the primary outcome, a two-sided Student's t-test will be used to compare

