the time to extubation between the two groups. If necessary, covariate adjustment will be made using the multiple linear regression analysis method. Differences between means and 95% confidence intervals will be estimated to describe the magnitude of intervention difference between the two groups. As part of sensitivity analyses, the time-to-extubation outcome will be also analyzed by the Cox regression model. To compare the categorical adverse events between two groups, chi-square test or Fisher's exact test will be used.

Missing Data: Prevention is the most obvious and effective manner to control bias and loss of power from missing data. Therefore, several strategies (e.g., timely data entry and daily missing data report) will be imposed to limit the likelihood that missing data will occur during this study. This protocol will follow the intention to treat principle, requiring follow-up of all subjects randomized regardless of the actual treatment received.

Power analysis: Our 'in-house' historical data ($n = 73$) showed that after excluding outliers greater than the 80th percentile, patients undergoing isolated CABG demonstrated a mean of 8.39 hours to extubation (SD 2.89). Although we anticipate a Hawthorne effect demonstrating reduced time to extubation in both the active and placebo arms of the present study, we have conservatively chosen to maintain power based on historical data. We therefore estimate that 45 subjects per group will give us 90% power to detect a clinically relevant effect size of 2-hours difference between active and placebo groups at an alpha value of 0.05 using a two-sided two-sample t-test. To allow for post consent, pre-randomization study drop out, we will aim to enroll a total of 110 ($90 + 20 = 110$) subjects.

SECTION II: RESEARCH INVOLVING DRUGS, BIOLOGICS, RADIOTRACERS, PLACEBOS AND DEVICES

If this section (or one of its parts, A or B) is not applicable, check off N/A and delete the rest of the section.

A. RADIOTRACERS

 N/A

If NO, an FDA issued IND is required for the investigational use unless RDRC assumes oversight.

1. Check one: IND# *Write here* or RDRC oversight (RDRC approval will be required prior to use)

B. DRUGS/BIOLOGICS

 N/A

1. If an **exemption from IND filing requirements** is sought for a clinical investigation of a drug product that is lawfully marketed in the United States, review the following categories and complete the category that applies (*and delete the inapplicable categories*):

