If a patient fails the 30 minute CPAP criteria, the ICU intensivist will be immediately notified. Every attempt will be made to correct the underlying cause of CPAP failure, and a prompt reassessment will be made as deemed appropriate by the intensivist to reattempt CPAP versus continuing controlled mechanical ventilation.

It is estimated conservatively that the study personnel will randomize 3 patients per week allowing for data collection to be completed within 1 year of study commencement. Data analysis and dissemination of findings will be conducted over the subsequent 6 months by the study institution investigators per the publication plan below.

Blinded analyses of the data will be performed by the study investigators along with the departmental statistician in the Department of Anesthesiology at the Yale School of Medicine.

**Variables/Time Points of Interest:** The primary outcome is the time to extubation, which will be the duration from arrival to the ICU to the extubation time. Participants' blood pressure, heart rate, and chest tube output will be tracked from arrival to the CTICU until extubation per ICU protocol.

**Statistical Methods:** Baseline comparability. We expect that the randomization process will produce reasonably comparable groups. However, the adequacy of the randomization will be assessed by comparing the distribution of baseline demographic and clinical characteristics among the intervention groups. Comparability for continuous variables will be examined graphically and by summary statistics (means, medians, quartiles, etc.). Categorical variables will be examined by calculating frequency distributions.

**Proposed statistical test/analysis:** Positively skewed variables will be log-transformed prior to hypothesis testing. For the primary outcome, a two-sided Student's t-test will be used to compare the time to extubation between the two groups. If necessary, covariate adjustment will be made using the multiple linear regression analysis method. Differences between means and 95% confidence intervals will be estimated to describe the magnitude of intervention difference between the two groups. As part of sensitivity analyses, the time-to-extubation outcome will be also analyzed by the Cox regression model. To compare the categorical adverse events between two groups, chi-square test or Fisher's exact test will be used.

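### Does leaving the scale of the primary analysis (log or hours) unstated undermine the comparison of time to extubation?

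*Protocol*

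**What the plan says.** The primary outcome is the time from ICU arrival to extubation. The analysis paragraph reads the same in the protocol (Section I, item 13, Proposed statistical test/analysis) and in the SAP under the same heading. It has three relevant steps, in this order:

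- a general rule: "Positively skewed variables will be log-transformed prior to hypothesis testing";
- the primary test: "For the primary outcome, a two-sided Student's t-test will be used to compare" the two arms;
- the estimate: "Differences between means and 95% confidence intervals will be estimated to describe the magnitude of intervention difference between the two groups".

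A Cox model of the same outcome follows as a sensitivity analysis.

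The power paragraph, also the same in both documents, is in untransformed hours. It takes a mean of 8.39 h and an SD of 2.89 h from 73 historical isolated-CABG patients, after values above the 80th percentile were dropped. The target is a "clinically relevant effect size of 2-hours difference between active and placebo groups", with 90% power and 45 per group "at an alpha value of 0.05 using a two-sided two-sample t-test".

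The SAP adds: "Blinded analyses of the data will be performed by the study investigators along with the departmental statistician". Neither document says how skewness is judged, whether time to extubation counts as skewed, or on which scale the difference and its interval are reported.

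**The concern.** Time to extubation usually has a long right tail, and dropping the top fifth of the historical values as outliers suggests that it does here. The log rule will therefore probably apply, and the t-test will then compare geometric means as a ratio. The only effect size in the plan is a difference in hours, so a reader may expect an interval in hours. That interval does not belong to a log-scale test. The trial's single primary result could then show p below 0.05 beside an interval that includes zero.

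The choice of scale also depends on a judgement about skewness with no stated threshold. If someone could choose the scale after seeing which one gave the smaller p-value, the nominal 5% would no longer hold.

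**Working it through.** **Step 1: the plan's own figure.** Inputs from the power paragraph: difference 2 h, SD 2.89 h, two-sided alpha 0.05, power 90%.

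- Standardised effect: 2/2.89 = 0.692.
- Normal approximation: n = 2 × (1.960 + 1.282)² / 0.692² = 43.9, so 44 per group.
- Noncentral t: 44.86, so 45 per group, with power 90.1% at 45.

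The stated 45 reproduces, on the hours scale.

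**Step 2: the same inputs on the log scale.** The documents give no distribution. I assume lognormal times with the plan's mean and SD.

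- Log-SD = √ln(1 + (2.89/8.39)²) = √ln(1.1187) = 0.335.
- Log-mean = ln 8.39 − 0.335²/2 = 2.071.
- Two hours off 8.39 h is a ratio of 6.39/8.39 = 0.762, a log difference of 0.272.
- Standardised effect: 0.272/0.335 = 0.813. Noncentral-t power at 45 per group is 96.8%, and 33 per group would give 90%.

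On these inputs, moving to logs does not cost power.

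**Step 3: what the unstated cut-off does.** Simulation with 40,000 trials per scenario, 45 per arm and a pooled-variance t-test, under the same lognormal assumption. The effect is either a proportional reduction (ratio 0.762) or a 2-hour shift.

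| | No effect | Ratio 0.762 | 2-h shift |
|---|---|---|---|
| Rejects, hours | 5.1% | 95.9% | 89–90% |
| Rejects, log | 5.1% | 96.8% | 96% |
| Rejects, log only if pooled skewness > 1 | 5.1% | 96.4% | 92% |
| Pooled skewness > 0.5 | 90% | 93% | 79% |
| Pooled skewness > 1 | 39% | 46% | 26% |
| Log test and hours interval disagree | – | 1.7% | 6.5–6.8% |

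A cut-off of 0.5 also leaves type I error at 5.1%. The Monte Carlo standard error there is √(0.05 × 0.95/40,000) = 0.11 percentage points, and repeat runs gave 4.9% to 5.2%. The cut-off does affect which scale is used, but it does not affect the error rate, and power never falls below that of the hours test on which the trial was sized.

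**Step 4: a heavier tail.** Suppose instead that the plan's figures describe only the lower 80% of a lognormal. Solving for that gives log-mean 2.235 and log-SD 0.501, hence a full mean of 10.6 h and SD of 5.7 h. Two hours is now a ratio of (10.6 − 2)/10.6 = 0.811.

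- Power for a proportional 2-hour reduction is about 45% in hours and 49–50% on logs. That drop comes from the larger spread and not from the choice of scale.
- A log test and an hours interval disagree in about 11% of trials (ratio 0.811) and 24% (2-h shift).
- Pooled skewness exceeds 0.5 in about 99% of trials and exceeds 1 in roughly 75–83%.

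So where the two scales disagree most, either cut-off usually selects logs, and the missing threshold matters less.

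**Step 5: the worst case.** If an analyst took whichever scale was significant, type I error would be 5.7% (Step 2 inputs) to 6.4% (Step 4 inputs). The plan does not propose this.

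**The case for a change.** The best argument for amending the plan is that this is the only stated efficacy outcome, that a few sentences would settle the matter, and that the blinded analysis leaves time to write them. The log rule is conditional and never names time to extubation. Even if the test is clearly on logs, nothing is said about back-transforming or about a ratio of geometric means, while the clinical target is in hours. When a log test and an hours interval disagree, in 71–99% of cases the log test is significant and the hours interval includes zero. Under a 2-hour shift, a cut-off rule also gives up 1 to 5 points of power compared with always using logs.

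Part of this stands. The scale is not named, and a sentence on back-transformation would be tidy. The rest carries less weight:

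- The mismatch needs a pairing that the plan does not call for. A t-test and the confidence interval from that same t-test always agree.
- The 1 to 5 points are measured against the most powerful option, and the rule still matches or beats the hours test that justified 45 per group. Under proportional effects the gap is about 0.7 points or less.
- The planned blinding of the analysis limits the scope for choosing a scale by its result, although arms under coded labels could still be compared.
- The Cox analysis uses only the ordering of times, so it gives the same answer in hours or logs and provides a check on the primary result.
- Fixing logs whatever the data show would demote the 2-hour difference that the plan calls clinically relevant. Fixing hours would remove the ambiguity equally well. This is a trade-off, and neither choice corrects an error.

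**Conclusion.** The omission is real but minor: a missing detail that a competent analyst fills in the usual way. Time to extubation is logged if skewed, the t-test is run, its interval is back-transformed to a ratio, and the difference in hours is shown alongside for clinical reading. That follows from the order of the plan's own sentences.

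No inflation of type I error is shown (about 5% with a cut-off of 0.5 or 1), and there is no loss against the planned 90% on the plan's mean and SD (92% or more). Only the unplanned pairing of a log test with an hours interval produces conflicting results, in about 2% to 7% of trials on those inputs and about 11% to 24% with the assumed heavier tail.

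The skewness percentages, log-scale power and disagreement rates all rest on an assumed lognormal shape, because the documents give no distribution and no untrimmed SD. Whether the trimmed SD is a fair planning value is a separate question from the choice of scale. No change to the plan follows.

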2. Patients will be transferred to the CTICU intubated and on a propofol infusion and/or dexmedetomidine (Precedex) from the operating room. Both meds are used SOC.
3. Upon CTICU arrival, the patients surgeon and CTICU intensivist will determine if patient is able to proceed with fast-track extubation. Determination of continued eligibility based on the post-recruitment pre-randomization exclusion criteria will be determined by a member of the study team. Eligible patients will be randomized, investigational pharmacy will be contacted for study drug and within 30 minutes of the ICU admission, propofol will be discontinued. Precedex may be continued per clinical discretion.
4. The participant will be randomized to receive Sugammadex or placebo. The enrolled patients will be assigned to the study and control arms in a 1:1 ratio.
5. IDS will provide the Sugammadex (2mg/kg) vs. Placebo in a syringe. A qualitative train-of-four measurement will be obtained. The administration of the study drug and placebo compounds will be performed by CTICU nurses who will receive the drugs in a blinded fashion from the departmental research pharmacy. The study drug will be supplied by Merck.
6. The clinical care provider has the discretion to determine the appropriate ventilation settings on a case-by-case basis, in accordance with the suggestion that patients will be initiated on SIMV rate of 14 with 60% FiO₂, tidal volumes 8-10 ml/kg and PEEP of 7.
7. Ten minutes after the drug administration, if the patient can lift their head and remains hemodynamically stable, the patient will be switched to CPAP mode of ventilation for 30 minutes. At the end of the CPAP trial tidal volumes, Rapid Shallow Breathing Index (RSBI) and ABG will be assessed. The patient will be extubated if he/she is not hypoxic/ hypercarbic, has RSBI<100 and has TV >300 cc.
8. If a patient fails the 30-minute CPAP criteria, the ICU intensivist will be immediately notified. Every attempt will be made to correct the underlying cause of CPAP failure, and a prompt reassessment will be made as deemed appropriate by the intensivist to reattempt CPAP versus continuing controlled mechanical ventilation.

Study participation will end when the patient is successfully extubated. AE assessment will be performed in the period immediately following extubation.

5. Genetic Testing N/A

6. **Subject Population:** Provide a detailed description of the types of human subjects who will be recruited into this study.

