4. Determination that the patient will require prolonged mechanical ventilation possibly requiring muscle relaxation based on the intraoperative course and clinical judgment of the study PI or collaborating intensivists.
5. Intraoperative hypoxia or on arrival to the ICU. (Please see Study Flowchart).
6. Cardiac arrest
7. Sudden arrhythmia (Ventricular tachycardia runs/sudden bradycardia with improper pacemaker detection/function) precluding fast-track extubation protocol.
8. Need for two or more inotrope initiation precluding fast-track protocol. Only a single vasopressor/inotrope may be initiated without excluding the subject.
9. Postoperative ST changes.

10. A positive standard of care pregnancy test during your pre-operative evaluation

9. How will **eligibility** be determined, and by whom?

Eligibility at pre-op and post-op will be based on protocol specific inclusion and exclusion criteria and will be determined by the PI or Sub-I's in collaboration with the ICU attending physician

10. **Risks:** Describe the reasonably foreseeable risks, including risks to subject privacy, discomforts, or inconveniences associated with subjects participating in the research.

Sugammadex is generally safe and well tolerated. Potential risks associated with sugammadex are: hypersensitivity, including anaphylaxis/anaphylactic shock – previous trials suggest this risk is small. Cardiac arrhythmias including bradycardia & tachycardia where intervention is rare and responsive to usual treatment. Other reported risks include nausea, vomiting, constipation.

Bleeding was originally thought to be a side effect, but studies have since showed that Sugammadex falsely elevates the PTT without increasing bleeding risk. (see reference on last page.)

11. **Minimizing Risks:** Describe the way the above-mentioned risks will be minimized.

Patients will all be in a critical care environment and monitored very closely including: blood pressure, heart rate, and chest tube output will be tracked from arrival to the CTICU until extubation per ICU protocol. Subtle changes in the patient's hemodynamic status are easily seen and treated if necessary.

12. **Data and Safety Monitoring Plan:** Include an appropriate Data and Safety Monitoring Plan (DSMP) based on the investigator's risk assessment stated below. (Note: the HIC will make the final determination of the risk to subjects.)

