**Missing Data:** Prevention is the most obvious and effective manner to control bias and loss of power from missing data. Therefore, several strategies (e.g., timely data entry and daily missing data report) will be imposed to limit the likelihood that missing data will occur during this study. This protocol will follow the intention to treat principle, requiring follow-up of all subjects randomized regardless of the actual treatment received.

**Power analysis:** Our 'in-house' historical data ( $n = 73$ ) showed that after excluding outliers greater than the 80th percentile, patients undergoing isolated CABG demonstrated a mean of 8.39 hours to extubation (SD 2.89). Although we anticipate a Hawthorne effect demonstrating reduced time to extubation in both the active and placebo arms of the present study, we have conservatively chosen to maintain power based on historical data. We therefore estimate that 45 subjects per group will give us 90% power to detect a clinically relevant effect size of 2-hours difference between active and placebo groups at an alpha value of 0.05 using a two-sided two-sample t-test. To allow for post consent, pre-randomization study drop out, we will aim to enroll a total of 110 ( $90 + 20 = 110$ ) subjects.

Per-protocol Sensitivity Analysis: In parallel with the primary analysis, if exclusions above occur post randomization but prior to drug administration, the investigators will conduct a parallel "per-protocol" sensitivity analysis.

Drug supplies will be supplied by the sponsor.

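### The stated 90% power uses an SD computed after deleting the slowest fifth of historical patients, while the trial analyses everyone randomized

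*Protocol*

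**What the plan says.** **Power.** Protocol Section I, 13 (Power analysis) uses 73 in-house historical patients: "after excluding outliers greater than the 80th percentile, patients undergoing isolated CABG demonstrated a mean of 8.39 hours to extubation (SD 2.89"). It continues: "We therefore estimate that 45 subjects per group will give us 90% power to detect a clinically relevant effect size of 2-hours difference", by a two-sided two-sample t-test at alpha 0.05. The SAP repeats the claim ("We therefore estimate that 45 subjects per group will give us 90% power"). Twenty further patients, making 110, are added only for losses between consent and randomization.

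**Analysis.** Under Missing Data: "This protocol will follow the intention to treat principle, requiring follow-up of all subjects randomized regardless of the actual treatment received". The endpoint runs from ICU arrival to extubation with no upper limit. Patients who fail the CPAP trial may stay ventilated (Section I, 4, item 8), and their times count. The SAP's per-protocol analysis is a sensitivity analysis and does not trim the primary one.

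**Screening before randomization.** Section I, 4, item 3: "Upon CTICU arrival, the patients surgeon and CTICU intensivist will determine if patient is able to proceed with fast-track extubation". Section I, 8 then lists exclusions, among them "Determination that the patient will require prolonged mechanical ventilation possibly requiring muscle relaxation based on the intraoperative course and clinical judgment".

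**Two related statements.** The authors call their choice conservative: "Although we anticipate a Hawthorne effect demonstrating reduced time to extubation in both the active and placebo arms of the present study", they keep the historical figures. On the scale of analysis: "Positively skewed variables will be log-transformed prior to hypothesis testing".

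**The concern.** The historical SD was computed after removing patients because their outcome was long (on the natural reading that the percentile is of time to extubation). The trial cannot do this: its screening comes before the outcome is known, and everyone randomized stays in the analysis. Where a distribution has a real upper tail, cutting it off lowers the SD, and a lower SD raises calculated power.

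The 90% figure is the only justification offered for 45 per group. If even part of the deleted tail is randomized, a true 2-hour benefit would be missed more often than the stated 1 time in 10. A null result would then be read as coming from a better-powered trial than the documents can show.

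**Working it through.** **Inputs from the documents.** n = 45 per arm; difference 2 h; SD 2.89 h and mean 8.39 h after the cut; two-sided alpha 0.05; planned losses before randomization 20 of 110. The untrimmed SD is not given.

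**1. Reproduce the plan's figure.** Noncentrality = 2 / (2.89 × √(2/45)) = 3.283, with 88 degrees of freedom and critical value 1.987. Power = 90.1%. The stated figure is reproduced.

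**2. Headroom.** Solving the same formula for the SD, power is 90% at SD 2.894 h and 80% at SD 3.349 h.

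**3. A bound that assumes no shape.** Suppose the whole deleted fifth is randomized, and let it have mean m and variance v. Then

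full variance = 0.8 × 2.89² + 0.2 × v + 0.8 × 0.2 × (m − 8.39)².

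Setting v = 0 gives the smallest possible variance, 6.682 + 0.16 × (m − 8.39)²:

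- SD exceeds 2.894 h (power below 90%) once m is at least 11.65 h.
- SD exceeds 3.349 h (power below 80%) once m is at least 13.71 h.
- At m = 15 h, SD is at least √(6.682 + 0.16 × 6.61²) = 3.70 h and power at most 72%.

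**4. Assumed shapes.** Each shape below is solved so that the part under its own 80th percentile has mean 8.39 h and SD 2.89 h. The middle columns restore the whole tail. The last three cut at the 90th percentile, as if screening removed exactly the slowest half of the deleted patients.

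| Shape | SD, whole tail in | Power, raw | Power, log | SD, slowest half out | Power, raw | Power, log |
|---|---|---|---|---|---|---|
| Normal | 3.78 h | 70% | – | 3.19 h | 84% | – |
| Gamma | 4.70 h | 51% | 56–75% | 3.44 h | 78% | 76–84% |
| Lognormal | 5.67 h | 38% | 50–72% | 3.60 h | 74% | 77–86% |

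The log-scale ranges cover two target ratios: (mean − 2)/mean, using the mean of the assumed distribution (lower figure), and 6.39/8.39 = 0.762, from the documented trimmed mean (upper figure). If screening removes a random half of the tail instead of the slowest half, raw power is 77%, 63% and 50%.

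**5. How good must screening be?** With a cut at the 83rd percentile, so that nearly the whole tail is removed, the normal shape gives 88.5% raw. The lognormal gives 86% raw and 88–90.1% on the log scale.

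**6. How large must the Hawthorne effect be?** The proportional fall in SD that restores 90% for 2 h on raw hours is 1 − 2.894/SD: 24%, 38% and 49% (normal, gamma, lognormal) with the whole tail in, and 9%, 16% and 20% with the slowest half out.

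**7. Detectable difference at 90%.** This is (2/2.894) × SD = 0.691 × SD: 2.6 to 3.9 h with the whole tail in, and 2.2 to 2.5 h with the slowest half out, against 2.0 h stated.

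**8. An unclear input.** If 73 is the count before the cut, about 0.2 × 73 ≈ 15 patients were deleted. If it is the count after, about 73/0.8 − 73 ≈ 18 were.

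**The case against.** The strongest reply is that screening does the same work as the trim. The fast-track decision and the exclusions act once the intraoperative course is known, and consent-stage exclusions act earlier still. The planned loss, 20/110 = 18.2%, is close to the deleted 20%. If those losses were exactly the slowest patients (a cut at 81.8%), power would be 88–89% on raw hours for all three shapes, 87–88% on the log scale for the gamma and 90–91% for the lognormal.

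It can also be said that the 51% and 38% figures apply a raw-hours test to skewed data that the plan would log-transform, that a common weaning pathway and optional covariate adjustment may reduce the SD, and that the reported 95% confidence interval will show the precision achieved.

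Much of this stands as a limit on size. The whole-tail figures are a worst case and do not forecast this trial. A short tail, with deleted patients averaging about 11 h and little spread, would also leave power near 90%. But the 18.2% case needs perfect foresight about extubation time, while several exclusions (bleeding, temperature, ST changes) do not measure it. The plan offers the 20 losses only as an enrolment allowance, never as a counterpart to the trim. The log transform recovers part of the loss, but no log-scale power or target ratio is given. The Hawthorne effect is not quantified. A confidence interval reported at the end does not make the planning figure correct.

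**Conclusion.** The concern holds. The arithmetic is correct, but the SD is not shown to describe the patients who will be analysed, so 90% is unsupported and probably optimistic.

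The firm results are the thresholds: below 90% above SD 2.894 h and below 80% above about 3.35 h. If the whole tail is randomized and hours are tested untransformed, power is below 90% once the deleted patients averaged about 11.7 h, whatever the shape. The other figures rest on assumed shapes and on how much of the tail screening removes: about 74–86% with the slowest half removed, and about 90% only if nearly all of it is removed or the SD falls materially for another reason. True power cannot be fixed from the documents.

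Two further gaps have no known direction and do not support the word optimistic. Power is calculated in hours although a skewed outcome would be tested on the log scale. And the SD comes from isolated CABG, while the trial now also admits AVR and AVR with CABG.

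**What to change.** - Recompute the SD from the in-house data without trimming on the outcome, among historical patients who meet the protocol's own eligibility and pre-randomization criteria, including AVR and AVR/CABG if available.
- Do so on the scale to be tested. If that is log hours, state the target as a ratio.
- State whether 73 is the number before or after the exclusions.
- In both the protocol and the SAP, replace the 90% with the power that 45 per group then gives, or with the difference or ratio detectable at 90%.
- Say that the choice is conservative only with respect to the Hawthorne effect.

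The cost is one re-run of existing data and one reworded paragraph in each document. The stated power may look less favourable. No extra patients and no change of test are needed.
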